### Secondary Efficacy Analysis:

#### *Secondary endpoints involving a proportion:*

Missing data for the secondary endpoints involving a proportion will be imputed using the same approach as described for the primary efficacy analysis (ICE handling and missing data imputation).

MAR imputation for the secondary endpoints involving a proportion will be generated based on a regression model with covariates for treatment group and the randomization stratification variable. Where appropriate, the dichotomous variable will be derived based on the imputed data.

#### *Change from baseline secondary endpoints:*

Handling of missing data of change from baseline in participants without ICES:

- Multiple imputation of the value at Week 24 (for BCVA and CST) assuming missing at random (MAR).

Handling of missing data of change from baseline after ICES:

- Single imputation using the worst value at each visit observed among all participants when applying composite variable strategy.
- Multiple imputation assuming MAR when applying treatment policy or hypothetical strategy.

Handling of data observed after ICES:

- The value will be replaced by a single imputation using the observed worst value at each visit among all participants when applying composite variable strategy.
- Replaced by MAR multiple imputation algorithm based on the assumption that the intercurrent event would not have occurred when applying hypothetical strategy.
- Kept in the analysis when applying treatment policy strategy.

MAR imputation for the continuous secondary endpoints (BCVA and CST) will be generated based on a linear regression model adjusting for treatment group, the randomization strata, and BL score of the analyzed variable where applicable and then the change from baseline will be calculated. A total of 100 imputations will be used followed by the MIANALYZE procedure to combine the estimates.

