2.21.2.2 Analyses of Secondary and Other Efficacy Endpoints

Estimands for the secondary endpoint analyses will be described in the SAP.

The secondary endpoints involving proportions of participants will be analyzed using the same approach (MH test) as described for the primary efficacy analysis and based on the ITT.

Time to event secondary endpoints will be analyzed using a stratified log-rank test adjusting for the randomization stratification factor.

Continuous secondary endpoints involving change from BL will be analyzed using an analysis of covariance (ANCOVA) model with BL measurement of the variable as a covariate and treatment group and the randomization stratification factor as fixed factors. The pair-wise comparisons of each OTT166 dose group versus combined vehicle control will be done in the ANCOVA model. Two-sided 90% confidence intervals for the difference of each OTT166 dose group minus combined vehicle control will be calculated. Additional details on

sensitivity analyses and missing data imputation of the secondary endpoints will be provided in the SAP.

Analyses of exploratory imaging outcome measures will be described in the SAP.

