**3.2.2 Primary Efficacy Endpoint and Estimand**

The primary efficacy outcome measure of the study will be the proportion of participants who have improved by  $\geq 2$  steps from baseline at Week 24 as determined by central reading center assessment using the DRSS. The primary clinical question of interest is to determine the effectiveness of different doses of OCT166 versus vehicle control on  $\geq 2$  steps improvement from BL in DRSS score at Week 24 without requiring rescue treatment if the study drug is not discontinued prior to Week 24. This will support the dose selection for subsequent pivotal studies of OTT166. The estimand for the primary efficacy analysis is defined as follows:

|   | Primary Estimand  |
|---|--|
| Treatment conditions of interest | OTT166 5 mg/day, OTT166 10 mg/day and matching vehicle control   |
| Participant Population           | DR participants with Type 1 or Type 2 diabetes under adequate control (HbA1c $\leq 12.0\%$ ) who show typical fundus alterations and have been diagnosed with moderately severe to severe NPDR or mild PDR as defined by the DRSS Steps 47, 53, and 61B, with BCVA $\geq 69$ ETDRS letters, CST of $\leq 325 \mu\text{m}$ , and a normal foveal contour. |
| Endpoint                         | $\geq 2$ steps improvement from BL in DRSS score at Week 24  |
| Population level summary         | Difference in proportion of participants achieving $\geq 2$ steps improvement from BL in DRSS score at Week 24 between each OTT166 treatment group and the combined vehicle control group.   |

|   | Primary Estimand  |
|---|--|
| Intercurrent events (ICEs) and strategies to handle ICEs | 
a) Rescue treatment in the study eye due to worsening DRSS level to 65 or higher prior to assessment of DRSS at Week 24
Composite strategy (non-response)
 
b) Death prior to DRSS assessment at Week 24
Hypothetical strategy
 
c) Use of rescue treatment in the study eye for any other reason prior to DRSS assessment at Week 24
Composite strategy (non-response)
 
d) Premature discontinuation of study drug for any reason prior to DRSS assessment at Week 24
Hypothetical strategy
 
e) Study drug compliance <75% through Week 24
Treatment policy strategy
 
f) Study drug compliance between 75% to <90% through Week 24
Treatment policy strategy
 |

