|   | ICE(s) with a composite variable strategy take priority over ICEs with other strategies. And ICEs with a hypothetical strategy take priority over ICEs with treatment policy strategy.   |

A Supplemental Estimand will be defined and analyzed where the ICEs defined above will be handled using alternative strategies as follows: c and e are changed to Hypothetical strategy.

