## 4.10 Efficacy Evaluation

### 4.10.1 Analysis and Data Conventions

This study is designed to evaluate the superiority of two doses of OTT166 (5 mg/day and 10 mg/day) compared to vehicle control for the treatment of DR. For each dose within each endpoint, the null hypothesis is that there is no difference between OTT166 and vehicle control or the difference is in the direction of inferiority of OTT166, and the alternative hypothesis is that there is a difference between OTT166 and vehicle control in the direction of superiority of OTT166.

All statistical tests will be one-sided and will be performed at the 5% level of significance, unless otherwise stated. The vehicle control group will be combined for all efficacy analyses and two-sided 90% confidence intervals will be presented. A comparison between the two control groups will be performed for the primary endpoint to confirm the groups are comparable.

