The time to event secondary endpoints will be defined as time to first development of an event and will be estimated based on the Kaplan-Meier method, along with a 90% confidence interval. Analyses will be based on observed data, where participants who receive rescue medication will be censored at the start of rescue medication. A stratified log-rank test adjusting for the randomization stratification factor will be performed, to compare the combined vehicle control with each treatment group. Additionally, a stratified Cox proportional hazards model adjusting for the randomization stratification factor will be employed to estimate the hazards ratio between the combined vehicle control and each treatment group.

Continuous secondary endpoints involving change from BL to Week 24 will be analyzed using an analysis of covariance (ANCOVA) model with BL measurement of the variable as a covariate and treatment group and the randomization stratification factor as fixed factors. As a sensitivity analysis of the continuous secondary endpoints involving change from BL to Week 24, a rank-based ANCOVA model will be employed. The pair-wise comparisons of each OTT166 dose group versus combined vehicle control will be done in the ANCOVA model. Two-sided 90% confidence intervals for the difference of each OTT166 dose group minus combined vehicle control will be calculated.

The specific reasons for meeting rescue criteria as described in protocol section 2.14.9 will also be summarized using number and percentage by treatment group.

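### Giving rescued eyes the worst BCVA or CST value of the visit and then comparing means inflates the standard error and, when rescue rates differ, scales the estimate by one eye

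*SAP*

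**What the plan says.** SAP 4.10.1.2, under the change-from-baseline secondary endpoints, has two rules for the composite strategy. For data missing after an intercurrent event it prescribes: "Single imputation using the worst value at each visit observed among all participants when applying composite variable strategy". For data that were observed: "The value will be replaced by a single imputation using the observed worst value at each visit among all participants when applying composite variable strategy". A rescued participant's own reading is therefore discarded in either case.

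The section does not say which intercurrent events are composite for BCVA and CST. Protocol 2.21.2.2 promises this elsewhere: "Estimands for the secondary endpoint analyses will be described in the SAP". The only estimand table in the SAP, in 3.2.2, is for the DRSS endpoint. There, two events are composite: rescue in the study eye for DRSS 65 or higher, and "Use of rescue treatment in the study eye for any other reason prior to DRSS assessment at Week 24".

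SAP 4.10.3 sets the main analysis: "Continuous secondary endpoints involving change from BL to Week 24 will be analyzed using an analysis of covariance (ANCOVA) model". It adds: "As a sensitivity analysis of the continuous secondary endpoints involving change from BL to Week 24, a rank-based ANCOVA model will be employed". SAP 4.10.1 requires that "two-sided 90% confidence intervals will be presented".

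**The concern.** A worst-outcome composite carries ordinal information: a rescued eye did worse than the eyes that were not rescued. It does not say by how many letters or microns. The SAP supplies that amount by borrowing the most extreme reading at the visit from any of the arms, giving it to every rescued eye, and averaging.

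This has two consequences. The spread within each arm grows with the square of the distance to the extreme eye, so the interval widens even when rescue is balanced. When rescue is not balanced, the mean difference is multiplied up by that same distance. The extreme eye may sit in the QID arm and still drive the BID comparison. The resulting figure in letters or microns describes nobody's change.

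The trial is meant to inform the choice of dosing frequency for Phase 3, and BCVA and CST differences by regimen would feed into that choice.

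**Working it through.** **1. The plan's own figure.** SAP 4.13 gives 66 completers per group for response rates of 0.26 and 0.06, one-sided alpha 0.05, 90% power, continuity-corrected chi-square. Uncorrected: n₀ = [1.645·√(2·0.16·0.84) + 1.282·√(0.26·0.74 + 0.06·0.94)]² / 0.20² = 55.7. Corrected: (n₀/4)·[1 + √(1 + 4/(n₀·0.20))]² = 65.3, so 66, with power 0.903. The figure reproduces. The documents give no power, SD or rescue rate for BCVA or CST. Only the group size (70) and the alpha carry over.

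**2. The estimate.** Let p_A and p_V be the rescued shares, m_A and m_V the mean changes in non-rescued eyes, and W the imputed change. Then

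D = (1 − p_A)·m_A − (1 − p_V)·m_V + (p_A − p_V)·W.

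With equal shares W drops out. Assume m_A = −12 µm, m_V = 0, p_A = 0.05, p_V = 0.10. Then D = −11.4 − 0.05·W.

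Two assumptions about rescued eyes at Week 24 bracket the result:
- They look like other eyes. Simulation gives D ≈ −14.7 µm, so W = (14.7 − 11.4)/0.05 = 66. With own values kept, D = −12.
- They worsen by 75 µm plus an exponential tail of mean 50 µm. Simulation gives D ≈ −23 µm, so W = (23 − 11.4)/0.05 = 232. With own values kept, D = −11.4 − 0.05·125 = −17.65 (about −17.5 simulated).

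**3. The standard error.** Within-arm variance = (1 − p)·σ² + p(1 − p)·(W − m)². Take σ = 25 and p = 0.05 in both arms:
- W = 66: vehicle 593.75 + 0.0475·66² = 800.7; active 593.75 + 0.0475·78² = 882.7; SE ratio √(841.7/625) = 1.16.
- W = 232: vehicle 3150.4; active 3421.7; SE ratio √(3286.1/625) = 2.29.

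Simulated results, one-sided 0.05, SE relative to a trial without rescue:

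| Rescue in both arms | Rescued eyes at Week 24 | SE ratio | Power, means | Power, ranks |
|---|---|---|---|---|
| 5% | like other eyes | 1.15 | 77% | about 81% |
| 5% | worsened, long tail | 2.3 | 36% | about 81% |
| 10% | like other eyes | 1.3 | 63% | 71–72% |
| 10% | worsened, long tail | 3.4 | 22% | 71–72% |

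For the 5% long-tail row, repeat simulations gave ratios of 2.1 to 2.3 and power of 36% to 42%. Measured against the same rescued eyes keeping their own values, the long-tail ratios are about 1.4 (5%) and 1.7 (10%).

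**4. A check with the ANCOVA itself.** BCVA, assumed SD of change 5 letters, no true effect, 70 per group, the extreme eye placed in QID, BID compared with combined vehicle.
- Seven rescued in every group: SE is 0.85 letters without the rule. With it, SE is 1.33, 1.66, 2.37 or 3.37 as the worst Week 24 score is 62, 55, 40 or 20, and the 90% half-width runs from 2.2 to 5.5 letters. Leaving the extreme eye (55, 40 or 20) in without copying it gives only 0.91 to 1.12.
- Seven rescued on vehicle and four on BID: the estimate is 0.81, 1.14, 1.77 or 2.69 letters over the same four scores. The rank-ANCOVA statistic stays between 0.40 and 0.43.
- The size follows from (difference in rescued counts / 70) × gap to the group mean. For example, 3/70 × 25 letters = 1.07 letters.

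**The case against.** The strongest reply is that a composite estimand counts rescue as a bad outcome on purpose, so a larger difference when vehicle has more rescue is partly the intended answer. That stands. A reader might set −23 µm against the assumed −12 µm and call the whole gap bias. The documents do not support that, because −12 µm is a no-rescue effect and a different estimand. What remains is that the size of the penalty is set by one eye and not by the estimand.

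The severe figures are one end of a range. Rescue is anti-VEGF and/or laser, and it can be triggered by DRSS, ASNV or investigator judgement without any CST rise. Rescued eyes may look ordinary at Week 24, and the loss is then modest (77% against 81%).

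Two stronger readings are tempting. One is that the worst value of the whole trial is used; the SAP rule is specific to each visit. The other is that one eye sets the estimate by itself. With equal rescue counts the simulated estimate stayed within 0.05 letters and 0.3 µm of zero in the seven-per-group case, and only precision suffered.

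Much is also already planned: a rank-based ANCOVA as sensitivity analysis, and medians within the endpoint definitions. These help, but they leave the main estimate and interval as they are. The supplemental estimand ("c and e are changed to Hypothetical strategy") sits with the primary endpoint and moves only rescue for reasons other than DRSS 65 or higher, so it does not cover this.

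**Conclusion.** The concern holds for the main analysis of BCVA and CST change. It rests on one inference: that rescue in the study eye is the composite event for these endpoints. The SAP does not say so, but rescue is the only event to which it gives a composite strategy.

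The mechanism follows from the formulas and needs no assumed inputs. The sizes do need them: SD of change, effect, rescue rates and the tail are all assumed, so only the ranges should be quoted. In the balanced scenarios tabulated above, ranks had more power than means, by a little or by a lot. With unequal rescue the mean difference was larger in size than with own values kept, by about 3 µm (−15 against −12) to 5.5 µm (−23 against −17.5).

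These are secondary endpoints with no multiplicity adjustment. The DRSS result, where rescue simply counts as non-response, is not touched. This is a change that should be made, but it does not threaten the trial's primary conclusion.

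**What to change.** In SAP 4.10.1.2 and 4.10.3:
- State that rescue in the study eye, for any reason, is the composite event for BCVA and CST.
- Make the rank-based ANCOVA, with rescued participants given the worst rank, the main test under that strategy, and report medians by arm. State its sidedness: SAP tests are one-sided by default, but 4.10.3 specifies a two-sided p-value for the rank-based ANCOVA of the categorical endpoints.
- Report the mean ANCOVA with its 90% interval beside it as supportive, with rescue handled by the hypothetical strategy so that letters and microns stay interpretable.
- If the worst-value rule is kept anywhere, say whether worst means the raw reading or the change. A common raw value gives rescued eyes with better baselines a larger loss.

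Cost: the main result is no longer a mean difference in letters or microns. The rank analysis is already in the SAP, but the mean ANCOVA with hypothetical handling of rescue is an added analysis, not a swap, and it leans on the SAP's missing-at-random imputation. No new data are needed.

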#### *Time to event secondary endpoints:*

- Missing data for the time to event of secondary endpoints will be considered as censored. Participants who receive rescue medication will be censored at the start of rescue medication.

### **4.10.1.3 Multiple Comparisons/Multiplicity**

No multiplicity adjustment is planned for this study.

#### 4.10.1.4 Examination of Subgroups

The uniformity of the treatment effect for the primary efficacy variable will be examined for the following subgroups:

- Age (<65 years, ≥65 years)
- Gender (Male, Female)
- Race (White, Black or African American, Asian, Other)
- Ethnicity (Hispanic, Not Hispanic)
- BMI (Normal [ $<25 \text{ kg/m}^2$ ], Overweight [ $\geq 25$  to  $<30 \text{ kg/m}^2$ ], Obese [ $\geq 30 \text{ kg/m}^2$ ])
- HbA1C ( $\leq 7\%$ ,  $>7\%$ )
- Diagnosis of systemic hypertension (Y/N)
- Duration of Diabetes (<median, ≥median)
- Randomization strata (Screening DRSS:47 or 53 or 61B)
- Presence of fluid in the central subfield at Baseline (Y/N)

A forest plot with overall treatment effect included at the top will be provided.

#### 4.10.2 Primary Efficacy Analysis

The primary efficacy outcome measure of the study will be the proportion of participants who have improved by  $\geq 2$  steps from BL DRSS at Week 24. DRSS score levels will be recoded into 12 steps, provided by WRC.

Comparison of the primary endpoint will be made between each dose group and the combined vehicle control group using Mantel-Haenszel (MH) test of the difference in two proportions stratified by the randomization stratification factor (BL DRSS score 47 or 53 or 61B). The estimated MH risk difference will be summarized along with the two-sided 90% CI using MH stratum weights and the Sato variance estimator.

The primary efficacy analysis will be performed on the ITT Analysis Set, while the PPS will be used as a supplementary analysis. ICEs and missing data will be handled as described in [Section 4.10.1.2](#).

In order to assess the robustness of the study conclusions to the choice of imputation method, the following sensitivity analyses will be performed on the ITT Analysis Set and PPS for the primary endpoint:

- An observed case analysis where only observed responses will be used for analysis.  
Observed data after initiation of rescue medication will be set to missing.
- A LOCF analysis where missing post-baseline responses will be imputed using the LOCF procedure.  
Measurements after rescue will be imputed using the last observation prior to rescue treatment; a non-response will be imputed if no post-baseline measurements are available.

A supplementary analysis will be performed on the ITT Analysis Set and PPS for the primary endpoint to assess the time to improvement of  $\geq 2$  steps improvement from BL in DRSS score. Analyses will be based on observed data, where participants who receive rescue medication will be censored at the start of rescue medication (unless improvement of  $\geq 2$  steps improvement from BL in DRSS score is achieved prior to starting rescue medication). This analysis will be presented based on the Kaplan-Meier method, along with a 90% confidence interval. A stratified log-rank test adjusting for the randomization stratification factor will be performed, to compare the combined vehicle control with each treatment group. Additionally, a stratified Cox proportional hazards model adjusting for the randomization stratification factor will be employed to estimate the hazards ratio between the combined vehicle control and each treatment group.

The primary efficacy analysis will also be performed by Baseline subgroups in [Section 4.10.1.4](#), to assess the consistency of the treatment effect.

An additional sensitivity analysis may be performed to assess the proportion of participants with an improvement of  $\geq 2$  steps improvement from the Visit 2/Baseline visit in DRSS score if needed.

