#### 4.10.1.2 Handling of Missing Data and Data After Intercurrent Events

##### Primary Efficacy Analysis:

Handling of missing DRSS response at Week 24 data in participants without ICEs:

- Multiple imputation assuming missing at random (MAR).

Handling of DRSS response at Week 24 data missing after ICEs:

- Single imputation (non-response) when applying composite variable strategy.
- Multiple imputation assuming MAR when applying hypothetical and treatment policy strategy.

Handling of DRSS data response at Week 24 observed after ICEs:

- Replaced by non-response (single imputation) in the analysis when applying composite variable strategy.
- Replaced by MAR multiple imputation algorithm based on data from participants not affected by the respective ICE when applying hypothetical strategy.
- Kept in the analysis when applying treatment policy strategy.

If a participant experiences more than one ICE, ICE(s) with a composite variable strategy take priority over ICEs with hypothetical strategies, which take priority over ICEs with a treatment policy strategy.

MAR imputation will be generated based on a regression model for DRSS levels with covariates for randomized treatment group and the randomization stratification variable. DRSS response will be derived based on the imputed values. A total of 100 imputations will be used, followed by the MIANALYZE procedure to combine the estimates.

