#### 4.13 Determination of Sample Size

The study will enroll approximately 210 participants, 70 participants in each OTT166 treatment group and 35 participants per group into each matching vehicle control group and allowing for around 5% study attrition, this will ensure at least 66 participants per treatment group and combined vehicle control group.

For the primary endpoint of improvement by at least 2 steps from baseline on the DRSS at Week 24, completing 66 participants per group (active treatment BID, active treatment QID, combined vehicle control) through Week 24 will yield at least 90% power to demonstrate that the active treatment is superior to placebo using a 1-sided alpha of 0.05, provided that the true treatment effect (active treatment efficacy rate minus control efficacy rate) is at least 0.20 and the control efficacy rate is at most 0.06.

The sample size calculation was computed in nQuery 8.7 using a Chi square test for two proportions (continuity corrected).

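### The observed-case and LOCF runs in SAP 4.10.2 are offered as checks on imputation, but both also change how rescue counts, and no planned run explores systematic departures from MAR

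*SAP*

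**What the plan says.** **Primary analysis.** The estimand table in SAP 3.2.2 (also Protocol 2.21.2.1) gives rescue a composite strategy, that is non-response. This applies whether rescue follows worsening to DRSS 65 or higher (ICE a) or any other reason (ICE c). Death (ICE b) and premature drug discontinuation (ICE d) are hypothetical. Low compliance (ICE e and f) is treatment policy. Composite outranks hypothetical, which outranks treatment policy.

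Under SAP 4.10.1.2, even a Week 24 grade observed after rescue becomes a non-response. A grade observed after a hypothetical-strategy event is replaced by imputation. For grades missing after events, the rule is "Multiple imputation assuming MAR when applying hypothetical and treatment policy strategy", and plain missing data are also imputed under MAR. The imputation model for DRSS levels contains only randomized treatment and stratum, with 100 imputations.

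**Sensitivity runs.** SAP 4.10.2 states: "In order to assess the robustness of the study conclusions to the choice of imputation method, the following sensitivity analyses will be performed". Two runs follow.
- Observed case uses observed responses only, and "Observed data after initiation of rescue medication will be set to missing".
- LOCF carries the last grade forward, and "Measurements after rescue will be imputed using the last observation prior to rescue treatment". Non-response is imputed only when there is no post-baseline measurement.

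The other planned checks are the per-protocol repeat, time to improvement censored at rescue, an optional analysis from the Visit 2 grade, and a Supplemental Estimand that makes ICE c and e hypothetical. None of them varies the MAR assumption.

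**The concern.** A check on the imputation method should hold the estimand fixed and change only how missing outcomes are filled in. Here the rescue rule changes at the same time. The runs can move away from the primary result with no missing data at all, or stay close to it because two changes cancel. Either way, the stated reading of robustness to imputation does not follow.

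The assumption that most needs testing is MAR. It covers participants with missing Week 24 grades, deaths, and those who stop drug without rescue. Under Protocol 2.14.10.1, progression beyond DRSS 61 is itself a reason to stop drug, while rescue is something a participant qualifies for after consultation (Protocol 2.14.9). A participant who progresses and stops drug but is not given rescue falls under ICE d. That participant is then imputed from others in the same arm and stratum who did not have that event. At stake is whether the report can say how far such participants could differ from the imputed values before the conclusion changes.

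**Working it through.** **1. Design figures.** SAP 4.13 gives a test of whether active is "superior to placebo using a 1-sided alpha of 0.05", and says that "completing 66 participants per group" "will yield at least 90% power to demonstrate" this, provided the effect "is at least 0.20 and the control efficacy rate is at most 0.06". The rates are therefore 0.26 and 0.06, with mean 0.16.
- Uncorrected n = [1.645·√(2·0.16·0.84) + 1.282·√(0.06·0.94 + 0.26·0.74)]² / 0.20² = 55.7.
- With continuity correction, n = (55.7/4)·[1 + √(1 + 4/(55.7·0.20))]² = 65.3, so 66. Corrected power at 66 is 90.3%.
- 66/0.95 = 69.5, so 70 per compared group.

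The plan's figure reproduces. The rates 26% and 6% are used below only as a scale.

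**2. The rules side by side.**

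| Participant | Primary | Observed case | LOCF |
|---|---|---|---|
| Rescued (ICE a or c) | Non-responder, kept in denominator | Out of numerator and denominator | Last pre-rescue grade decides; non-response only if no post-baseline grade |
| Week 24 grade missing, no rescue | MAR imputation | Excluded | Last grade carried forward |
| Drug stopped without rescue, Week 24 grade observed | Replaced by MAR imputation | Not stated; only post-rescue data are set to missing | Not stated |

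The first row shows the change in estimand. The third shows that the handling of ICE d may change too.

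**3. Rescue rule, observed case, no missing data.** The documents give no rescue rate, so every share is an assumption.

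(a) Let 26% and 6% be the primary-analysis rates, with rescued participants in the denominators. Then observed case = 0.26/(1 − rA) − 0.06/(1 − rV), where rA and rV are the shares rescued on active and vehicle.
- 10%/20% rescued: 28.9% − 7.5% = 21.4 points.
- 5%/30% rescued: 27.4% − 8.6% = 18.8 points.
- The primary difference is 20 points in both cases.

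(b) Let 26% and 6% instead be the rates among non-rescued participants. Observed case is then always 20 points, and primary = (1 − rA)·0.26 − (1 − rV)·0.06.
- 10%/10% rescued: 23.4% − 5.4% = 18.0 points.
- 15%/5% rescued: 22.1% − 5.7% = 16.4 points.
- 5%/15% rescued: 24.7% − 5.1% = 19.6 points.

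**4. Rescue rule, LOCF.** On base (b), LOCF adds rA·qA − rV·qV to the primary difference, where q is the share of rescued participants whose last pre-rescue grade is a 2-step gain. At 10%/10% rescued it gives 18.0 points if no rescued participant has such a grade. It gives 18.8 if q is 10%/2%, and 20.0 if q is 26%/6%. Each such participant moves an arm of 70 by 1/70 = 1.4 points.

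**5. Departures from MAR.** Leave rescue aside, let a share m be missing in each arm, and let MAR give 26% vs 6%.
- Missing active participants imputed at the vehicle rate: (1 − m)·0.26 + m·0.06 − 0.06 = 0.20·(1 − m). This gives 19, 18 and 17 points at m = 5%, 10% and 15%.
- Extreme bound, with missing active all failing and missing vehicle all responding: 0.20 − 1.20·m. This gives 14, 8 and 2 points.

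Apart from rescue, observed case rests on essentially the same assumption as the imputation model: within arm and stratum, those with missing grades resemble those observed. LOCF applies a single different assumption. Neither traces the range between MAR and the bound.

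**The case against.** Four points on the other side have force.

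- **The MAR group is smaller than it may look.** A reader might infer that every drug discontinuer is imputed like a completer. The documents do not support that. Rescue requires stopping drug (Protocol 2.14.10.1), and composite outranks hypothetical, so rescued discontinuers are non-responders.
- **MAR is not wholly unchallenged.** LOCF is not a MAR method. Someone who leaves before gaining 2 steps is carried forward as a non-responder, as is someone with no post-baseline grade. The claim that stands is narrower: LOCF is one fixed alternative, mixed with a changed rescue rule, and does not explore departures systematically.
- **The LOCF rescue change is limited.** For ICE a, rescue follows a central grade of 65 or higher, and fundus photography is required before rescue (Schedule of Activities, footnote e). The last pre-rescue grade will normally be a non-response. The change matters mainly for ICE c, and only when the last pre-rescue grade is itself a 2-step gain; a gain since lost does not count.
- **The shift may be small.** At 5% missing, imputing at the vehicle rate costs 1 point. The 90% interval half-width at 26% vs 6% with 70 per arm is 1.645·√[(0.26·0.74 + 0.06·0.94)/70] = 9.8 points. This is a Phase 2 dose-selection study, and the Supplemental Estimand already varies the handling of ICE c.

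The last point lowers the urgency but does not repair the label. The Supplemental Estimand is presented as a different estimand; the two runs in 4.10.2 are not.

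A reader might also infer that observed case flatters the active arm. Its direction depends on the rescue shares, as 21.4 against 18.8 points shows.

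**Conclusion.** The concern holds in this form. Both runs offered as checks on imputation also drop the rule that rescue is non-response, so their agreement or disagreement with the primary result cannot be attributed to imputation. No planned run explores systematic departures from MAR for missing data, death or non-rescue drug discontinuation.

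The size cannot be fixed from the documents, which give no rescue rate and only about 5% planned attrition. Under the assumed shares above, the observed-case rescue rule moves a 20-point difference by about 1 point in either direction on base (a). On base (b), it lies 0.4 to 3.6 points above the primary result. Imputing missing active participants at the vehicle rate costs 1 to 3 points at 5% to 15% missing. At the full design effect, such modest departures would not by themselves overturn the result. They matter more if the effect is smaller or missingness is higher.

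Nothing here faults the primary estimand or the sample size.

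**What to change.** In SAP 4.10.2:

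1. Keep rescued participants (ICE a and c) as non-responders in both the observed-case and LOCF runs, so that only the handling of missing data changes. List any run with another rescue rule as supplementary, next to the Supplemental Estimand. State in both runs whether Week 24 grades observed after non-rescue drug discontinuation are used.
2. Add a delta-adjusted tipping-point analysis on the same 100 imputations. The SAP imputes DRSS levels and then derives response, so the shift can be applied in DRSS steps to imputed values before response is derived, with rescued participants left as non-responders. Report the shift at which the lower limit of the 90% interval reaches zero.

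Do not replace observed case with non-responder imputation as a sensitivity analysis of the primary estimand. That would move death and drug discontinuation from hypothetical to composite and so change the estimand again. If that run is wanted, label it supplementary.

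The cost is SAP wording and slightly more programming and reporting. No new data and no change in sample size are needed, and SAP 4.14 allows changes until database lock.
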